Labor and Delivery Implant Insertion (LADII)

[name]
[REDACTED], MPH
[name], MS
Stanford University

Phone: [REDACTED]
Email: [REDACTED]

Project Summary:

Investigating the timing to lactogenesis stage II (defined as the initiation of copious milk secretion) in women who obtain the contraceptive implant in delivery room versus the postpartum ward will add important data to the literature. If insertion in this time period is found to be without negative effects on breastfeeding the study findings would facilitate earlier insertion of the contraceptive implant, in the delivery room. Gurtcheff et al. recently analyzed time to lactogenesis in women initiating the contraceptive implant prior to medical discharge following delivery and 4-8 week postpartum and found no difference. In the proposed study, we seek to add to the literature by investigating immediate post-delivery insertion in the delivery room of the contraceptive implant versus insertion prior to medical discharge in the postpartum ward.

We propose a non-inferiority randomized controlled trial comparing time to lactogenesis stage II in healthy women with immediate insertion (0-2 hours following delivery) of the contraceptive implant in the delivery room versus in women with insertion of the contraceptive implant following delivery in the postpartum room and prior to medical discharge (24-48 hours following delivery). We hypothesize there will be no significant difference in time to lactogenesis with immediate delivery room (0-2 hours following delivery) vs. postpartum ward insertion (24-48 hours). In addition, we plan to follow women postpartum to evaluate breastfeeding continuation and exclusivity, discontinuation of the implant and any adverse events.

Description of the Project:

1.1 Rationale:

Over half of the 6.1 million pregnancies each year in the United States are reported as unintended. [1] More interventions are needed to prevent unintended pregnancies, as they are associated with higher maternal and child morbidity and mortality. [2] Infants conceived by women less than six months postpartum are at increased risk of poor perinatal outcomes such as being small for gestational age and being born preterm. [3] Additionally, both unintended pregnancy and a short inter-pregnancy interval are associated with delayed and insufficient prenatal care. [4] Gemmill et al. (2013) investigated the prevalence and correlates of short inter-pregnancy intervals in the United States. These authors documented that one third of pregnancies conceived in a nationally representative sample were within 18 months of a previous birth (n=2253). After adjusting for sociodemographic and childbearing characteristics, women were significantly more likely to have a short inter pregnancy interval if they were ages 15-19 years old. [5]

Further, pregnancies of adolescents (ages 10-18) and young women (ages 19-24) are very unlikely to be planned pregnancies. In fact, 82% of pregnancies were unplanned in the 15-19 age range. Robust data demonstrates that adolescent and young mothers are at high risk of becoming pregnant within 12 months of delivery--these mothers have a

higher risk of preterm birth, low birth weight and neonatal mortality compared to their adult counterparts.

There is evidence of adolescents who experience repeat pregnancy have poorer educational attainment and lower rates of employment than adolescents that do not have a repeat pregnancy. We also have data that young mothers who initiate LARC are less likely to have repeat pregnancies than those who decline postpartum contraception [6].

A 2015 survey of postpartum women about future pregnancy intention and contraception plans found the majority (n=237, 96.7%) of women did not desire pregnancy in the next year. [7]

Many women have already ovulated and resumed sexual intercourse by 6 weeks postpartum [8] and upwards of 40% of women do not return for postpartum care. [9] The majority of providers wait until the six week postpartum visit to initiate contraception—this delay in contraceptive uptake puts women at risk of an unintended, short interval pregnancy. An opportune time to facilitate contraception initiation is in the immediate postpartum period following delivery and prior to hospital discharge. Providing women with contraception they need during this time is convenient and cost effective for the patient, provider, and health care system. [10] In the 2015 survey of postpartum women, 42.8% (n=107) indicated that if the implant or intrauterine device could be inserted before they left hospital, they would choose these methods (p<0.0001). [7]

A 2009 CDC study analyzed the prevalence and types of contraception used by 43,887 women 2-9 months postpartum and found that 88% reported use of at least one contraceptive method, with 61.7% using a highly effective method, defined as: <10% of women experience an unintended pregnancy; includes sterilization, intrauterine device, shot, pill, patch, and ring. [11]

This same study demonstrated that women with no prenatal care had the lowest rates of using at least one method (76.9%) and had a low rate of using highly effective contraceptive methods (54.5%). Based on these data, the promotion of highly effective contraception, especially among women with no prenatal care, should be prioritized and immediate postpartum initiation of a highly effective method could be the solution. [11]

The World Health Organization (WHO) and the CDC have distinct recommendations with regard to early administration of the contraceptive implant. By the CDC Medical Eligibility Criteria for Contraceptive Use, the etonogestrel implant is classified as a Category 2 method for breastfeeding women at less than 1 month postpartum, indicating this is a method for which advantages generally outweigh any theoretical or proven risks. [12] However, the 5th edition of the WHO Medical Eligibility Criteria for Contraceptive use classifies the implant as category 2, indicating “generally use, some

follow-up may be needed” for women breastfeeding at less than 1 month postpartum. [13] These slightly different recommendations may have an impact on the availability of progestin-only methods for women in the postpartum period. More information is needed on the impact of the implant on breastfeeding immediately postpartum in order to inform improvements in service delivery and family planning interventions, both domestically and internationally.

In addition to this, a barrier to initiating progestin contraceptives in the early postpartum period is the concern of interference with breastfeeding, specifically lactogenesis. A study looking at lactation consultants' knowledge about postpartum contraception and impact on breastfeeding documented disconnect between the Centers for Disease Control (CDC) United States Medical Eligibility Criteria for Contraceptive Use (US MEC) guidance and lactation consultants' knowledge regarding the safety of immediate postpartum contraception. [14] Providing different recommendations amongst health care providers and lactation consultants may lead to confusion for patients—conflicting opinions regarding their contraceptive method may result in less women leaving the hospital without a method of contraception.

Duvan et al. (2010) showed that if women are well-informed regarding the side effects of the contraceptive implant, women find that it is an acceptable form of reversible contraception in the postpartum period. [15] The pharmacokinetic profile of the etonogestrel implant shows a peak serum concentration of approximately 1,000 pg/mL on day 4 after insertion. Thus insertion immediately postpartum should not interfere with lactogenesis, as there would still be a drop in progesterone that would allow for lactation induction to occur following delivery. [16], Appendix A

The initiation of the contraceptive implant at 4-8 weeks postpartum has been studied in breastfeeding women; no change in volume or composition of breast milk was found. [17] A study looking at growth of breastfed infants found that at three year follow up, child growth and development was no different between users of implant and copper intrauterine device (IUD). [18] Additionally, Brito et al. (2009) documented no diminished weight gain in infants of women who were exclusively breastfeeding and obtained a contraceptive implant at 6 weeks postpartum. [19] The literature demonstrates immediate contraceptive implant insertion does not alter volume of breast milk intake by newborns. Braga et al. (2015) evaluated breast milk volume when the ENG implant was inserted immediately postpartum and found no difference in the median breast milk intake by newborns between women who were randomized to have the implant inserted within 48 hours after delivery and those who obtained no method of contraception. The study also documented similar weights of newborns between both groups at six weeks following delivery, adding to safety data on effects of immediate insertion on breastfeeding. [20]

Objectives and hypotheses:

This is a non-inferiority randomized controlled trial:

Our objective is to determine whether time to lactogenesis stage II differs between immediate delivery room insertion (0-2 hours following delivery) and delayed postpartum insertion (24-48 hours following delivery) of the contraceptive implant in the postpartum ward prior to medical discharge. We hypothesize there will be no significant difference in time to lactogenesis stage II between the two groups.

Design & Methodology:

This is a non-inferiority randomized controlled trial.

Peripartum women with healthy, term newborns who plan to use the contraceptive implant (etonogestrel implant, Nexplanon) for postpartum contraception and intend to breastfeed will be randomized to receive:

- **Arm 1: Immediate delivery room insertion (0-2 hours following delivery)**
- **Arm 2: postpartum room insertion (24-48 hours following delivery)**

The primary outcome is time to lactogenesis stage II (defined as the initiation of copious milk secretion) as documented by maternal perception by a validated tool. [21]

Secondary outcomes include breastfeeding continuation and exclusivity, contraceptive continuation, patient satisfaction, pregnancy rates, timing and number of follow up postpartum care visits.

Data will be collected on time of exclusive breastfeeding in days, supplementation rates, side effects (irregular menstrual periods, changes in appetite, nausea, acne, headache) continuation or change of contraceptive method, dates of follow up postpartum care visits, subsequent pregnancies and user satisfaction. These data will be collected in the week following insertion, at 4-8 weeks, 3, 6, and 12 months following insertion with telephone interviews or online questionnaires.

Recruitment methods will take place in the clinical setting through chart review and provider referral. We will also use flyers placed on public announcement boards on campus and wherever permitted in the hospital.

Study Procedures:

Eligible women will be screened and identified via chart review, in the pre-natal obstetric clinic, and labor and delivery ward (L&D) at Stanford University by research study staff. If patients meet criteria, the treating physician will initially approach and inform patients about the study. If a patient is interested, the treating physician will notify research staff and the patient will be approached by research personnel to discuss participation. If a treating physician has identified a patient who may be eligible

for study recruitment and physician confirms that patient agrees to be contacted by phone, we will call the patient and conduct a telephone screening interview (please see attached materials) and will recruit the patient in person at their next prenatal visit or when admitted to Labor and delivery, prior to delivery.

Patients will be counseled about risks and benefits of contraceptive options and will be counseled appropriately regarding risks and benefits of subdermal contraception implant, as well as the unknown effects of early progestin administration on breastfeeding. Patients will not be eligible for the study unless they have been consented for a postpartum contraceptive implant prior active labor. If the patients meet inclusion criteria they will be invited to participate in the study and consent will be obtained. When a study patient is admitted to L&D, they will be met by research personnel and be randomized to one of the two arms. Participants will be randomized through block randomization—allocation will be sealed in an opaque envelope. The patient, provider, and research staff will be aware of arm allocation, this is not a blinded study. At this time, baseline data will be collected on patient age, gravidity, parity, breastfeeding experience on REDCap with a designated Ipad.

Trained providers will use standard protocol to place the contraceptive implant either in delivery room or in postpartum ward after delivery. We will collect information on the timing of delivery and the time of implant insertion. A card indicating date of insertion and expiry date will be given together with post insertion instructions on wound care. Participants will be monitored daily by the research staff, in the first seven days postpartum, or until lactogenesis reported, beginning at 24-hours following delivery, to determine time to lactogenesis stage II using a validated tool. [21] Patients will be asked: "Has your milk come in yet?" and "When did your milk come in?" If the patient answers yes to first question the response will be recorded to the nearest hour. Participants will be asked: "How many times have you tried to breastfeed before your milk came in? Delayed lactation will be defined as no lactation by 72-hours following delivery. Lactation failure will be defined as no lactogenesis by 120-hours following delivery. Post-discharge follow-up questionnaires will involve telephone interviews, text messaging, electronic communication as needed, until lactogenesis occurs and at 4-8 weeks, 3, 6, and 12 months. Participants will be asked about length of exclusive breastfeeding, supplementation rates, side effects, continuation or change of contraceptive use (including abstinence or withdrawal), dates of postpartum medical visits, pregnancy, satisfaction with the contraceptive implant, resumption of vaginal intercourse, and infant weight. Once the participant completes the 12 month follow up questionnaires, they will have completed the study.

Criteria for selection of subjects:

Exclusion criteria:

Contraindication to implant insertion such as history of breast cancer. Hypersensitivity to any components of implant. Women who are not English or Spanish speakers or fluent in either language. Women who delivery infants that are not healthy.

Inclusion criteria:

- Pregnant women who are patients of the Stanford University Obstetrics service
- Pregnant women who delivery a healthy infant, regardless of gestational age.
- Intend to breastfeed
- Desire the contraceptive implant as their method of contraception
- Agree to be randomized to delivery room vs. postpartum ward insertion

Description of the drugs & devices to be studied:

Not applicable.

Follow up procedure:

Participants will receive brief telephone follow-up, including an interview at 4-8 weeks, 3, 6, and 12 months from date of delivery.

Criteria for discontinuation:

Participants who experience complications during labor and delivery or whose infants have medical problems will be discontinued. Patients who change their mind about contraceptive implant use will be discontinued. Intention to treat analysis will be employed.

Lab and other investigations:

Not applicable.

Data Management

Data will be collected on REDCap software, will be coded, monitored, and verified.

Data Analysis

SPSS version 23 will be used for data analysis.

Number of subjects and statistical power:

Based on previous reports of women with uncomplicated vaginal deliveries, mean time to lactogenesis stage II is 54 hours with a standard deviation of 12 hours. [21] If there is truly no difference between immediate insertion and delayed insertion of the contraceptive implant on time to lactogenesis stage II, then 68 patients are required to be 80% sure that the lower limit of a one-sided 95% confidence interval (or equivalently a 90% two-sided confidence interval) will be above the non-inferiority limit of a mean difference of 12 hours (alpha 5%; SD 18). Sealedenvelope.com was used to calculate

sample size based on these parameters. A non-inferiority margin of 12 additional hours is chosen to be relevant because common medical interventions like epidural anesthesia, cesarean section, labor induction, have been to delay stage II lactogenesis by up to 12 hours. [22] To account for potential participant dropout, 82 participants will be recruited.

Study limitations:

This is not a blinded study; appropriate blinding would require the use of placebo implants and additional procedures. We do not anticipate our inability to blind participants and providers to impact our primary outcome of time to lactogenesis stage II.

Our recruitment will be limited to the Stanford Obstetrics and Gynecology service. Thus internal validity will not be a concern, but this clinic's population is not representative of the diversity of the female population in the United States or of women giving birth in the United States.

Based on this study's inclusion and exclusion criteria, results cannot be extrapolated to women with some medical conditions, complications, during labor and delivery, or who have infants with medical problems.

Duration of project:

Project completion is expected in 21 months. 9 months for recruitment, enrollment, and data collection, 12 months for follow up phone call, data analysis, and manuscript writing. Estimated Start and End date: September 2016 – June 2018.

Project management:

Project will be coordinated, conducted, and monitored by research staff. The research mentors will be: [name] M.D., M.S, primary mentor, and [REDACTED], MPH, secondary mentor.

Links with other projects:

Not applicable.

Main problems anticipated:

Our recruitment site sometimes experiences low patient volumes that may contribute to slow recruitment. It is possible that enrolled patients may experience complications during labor and delivery or after delivery in which case, patients will no longer be eligible for study. Patients may change their mind and no longer wish to participate in study. In order to mitigate these potential challenges, we will chart review in advance on a weekly basis in order to approach all eligible patients. We will also counsel and explain study thoroughly to ensure patients are able to make informed decisions regarding participation.

Expected outcomes of the study and dissemination of findings:

We expect to find that timing to lactogenesis stage II is not different between women who obtain contraceptive implant insertion in the delivery room versus in the postpartum ward. We hope to publish these results to contribute to body of literature that examines safety of immediate postpartum contraception, allowing for better delivery of postpartum contraception without negative effects to breastfeeding in the period of 1-2 hours after delivery.

References:

1. Finer LB and Zolna MR, Declines in unintended pregnancy in the United States, 2008–2011, *New England Journal of Medicine*, 2016, 374(9):843–852, <http://nejm.org/doi/full/10.1056/NEJMs1506575>.
2. Zhu, B.P: Effect of interpregnancy interval on birth outcomes: findings from three recent US studies. *Int J Gynecol Obstet*, 89 (Suppl. 1) (2005), pp. S25–S33
3. Zhu, B.P, R.T. Rolfs, B.E. Nangle, J.M. Horan. Effect of the interval between pregnancies on perinatal outcomes. *N Engl J Med*, 340 (8) (1999), pp. 589–594
4. Mayer JP¹. Unintended childbearing, maternal beliefs, and delay of prenatal care. *Birth*. 1997 Dec;24(4):247-52.

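### The protocol promises to evaluate any adverse events, but its text lists no adverse-event outcome and states no route for collecting insertion-site, procedural, early maternal or infant medical events, or for comparing them by arm

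*Combined protocol and SAP*

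**What the plan says.** The Project Summary commits to following women after delivery to evaluate, among other things, "discontinuation of the implant and any adverse events".

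Design & Methodology sets out the outcomes: "Secondary outcomes include breastfeeding continuation and exclusivity, contraceptive continuation, patient satisfaction, pregnancy rates, timing and number of follow up postpartum care visits". Adverse events are not in that sentence. The same section gives the one itemised safety list, "side effects (irregular menstrual periods, changes in appetite, nausea, acne, headache) continuation or change of contraceptive method", and the schedule: "These data will be collected in the week following insertion, at 4-8 weeks, 3, 6, and 12 months following insertion".

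Study Procedures restates what will be asked: "Participants will be asked about length of exclusive breastfeeding, supplementation rates, side effects, continuation or change of contraceptive use". Here the side effects are not itemised. The sentence goes on to dates of medical visits and ends with "resumption of vaginal intercourse, and infant weight". For the insertion itself, the section records the times of delivery and of insertion, and adds: "A card indicating date of insertion and expiry date will be given together with post insertion instructions on wound care". It also has staff ask daily about milk onset and defines delayed lactation (none by 72 hours) and lactation failure (none by 120 hours).

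Criteria for discontinuation removes women with labor or delivery complications and women whose infant has a medical problem. It calls for intention-to-treat analysis but does not say that these occurrences are recorded as events. Data Analysis names only the software.

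**The concern.** A stated aim needs three things downstream: a definition or outcome line, a question that captures the data, and a summary by arm. For adverse events in general, the text supplies none of the three clearly.

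The five listed effects also match the randomised contrast poorly. Both arms receive the same implant, at 0-2 hours or at 24-48 hours, and these effects are asked about out to 12 months. On my reading they are general effects of the implant, not items chosen to show a consequence of moving insertion by one to two days. What the arms differ in is the setting and timing of the procedure, so the procedure, the insertion site and the first days are the natural places to look for a difference.

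At stake is whether the final report can say anything about adverse events beyond breastfeeding and the five effects. Events from the first days cannot be reliably recovered once the early contacts have passed. Patients, providers and staff all know the allocation (Study Procedures), so reliance on spontaneous reports would also allow reporting to differ between arms.

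**Working it through.** The plan gives no figure on this point, so the main check sets each type of event against its stated route into the data.

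| Type of event | Stated route |
|---|---|
| Late or absent milk | Daily question; 72 h and 120 h definitions (Study Procedures) |
| Infant feeding and growth | Exclusive breastfeeding, supplementation, infant weight (Study Procedures) |
| Stopping the implant | Continuation item at each follow-up contact; no reason stated |
| The five listed effects | Itemised in Design & Methodology |
| Insertion-site or procedural problem | None stated, unless reported as a side effect; insertion time and wound-care advice only |
| Early maternal event leading to care | At most a visit date, without the reason |
| Infant medical visit or readmission | None stated; an infant medical problem leads to discontinuation |
| Any of these, compared by arm as adverse events | None stated |

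The first four rows are covered. The last four have no clear route.

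**Early contact.** Daily monitoring lasts seven days or until milk onset is reported, and its stated purpose is milk onset. Taking the mean onset of 54 h from the sample-size section and assuming that contact stops at onset, a typical woman would be followed daily for this long after insertion:

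- Delivery-room arm: 54 − 2 = 52 h to 54 − 0 = 54 h.
- Ward arm: 54 − 48 = 6 h to 54 − 24 = 30 h.

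Problems mentioned incidentally in those calls would be gathered over unequal windows after insertion. The planned contact in the week following insertion could even this out, but its stated content is the listed items.

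**What collection could show.** Inputs: 82 recruited and 68 required (Number of subjects and statistical power). Equal arms are assumed, giving 41 or 34 per arm. If no event of a given type occurs among n women, the exact one-sided 95% upper bound on its rate is 1 − 0.05^(1/n):

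- n = 41: 1 − 0.05^(1/41) = 0.0705, or 7.0%.
- n = 34: 1 − 0.05^(1/34) = 0.0843, or 8.4%.

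The chance of seeing at least one event in an arm when the true rate is 2% (an illustrative assumption) is 1 − 0.98^n, which is 0.56 for n = 41 and 0.50 for n = 34. A comparison of 5% with 20%, also illustrative, at two-sided 5% (normal approximation) has power of about 54% with 41 per arm and 46% with 34. The yield is therefore descriptive.

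**The case against.** The strongest reply is that the harm this trial was built around is impaired lactation, and that harm is measured closely. A reader might infer that nothing which could depend on delivery-room timing is asked about. The documents do not support that: delayed lactation, lactation failure, supplementation, infant weight and implant continuation could all depend on timing, and all are collected.

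A reader might also infer that safety questions are confined to the five effects. That goes too far. Study Procedures asks about side effects without repeating the list, and the parenthesis in Design & Methodology does not say that it is exhaustive. The wording of the actual questions would be in Appendix B, which is listed but not included in the public text. One can say that the protocol does not state the collection; one cannot say that the questions are never put.

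A third tempting step is that the trial will claim no safety difference on events it never sought. Expected outcomes of the study does aim to "contribute to body of literature that examines safety of immediate postpartum contraception", but the same sentence goes on to concern breastfeeding. No section plans a claim about insertion-site or maternal events.

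Finally, nothing in the documents suggests that such events differ between the two windows, and trained providers use the same standard procedure in both places. All of this stands, and it narrows the point. It does not answer the mismatch between the Project Summary's promise and the outcomes, items and analysis that follow. A visit date without a reason does not identify an event, and discontinuing a woman because of a complication does not record one.

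**Conclusion.** The point holds as a gap between a stated aim and its stated means. The protocol says it will evaluate any adverse events, but it does not list them as an outcome and itemises only five general implant effects. It does not state that insertion-site, procedural, early maternal or infant medical events are collected or compared by arm.

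The gap does not touch the validity of the primary analysis. Its size is limited by the sample: even complete collection with zero events would exclude only rates above 7.0% (41 per arm) or 8.4% (34 per arm), one-sided 95%, assuming equal arms. The change should still be made, because it is cheap and the early information is lost if it is not asked for in time. The conclusion rests on the protocol text alone. If Appendix B already contains the questions, what remains is the missing outcome line, the by-arm summary and a cross-reference.

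**What to change.** - **Design & Methodology, outcomes:** add *adverse events by arm (descriptive)* as a secondary outcome, with a short definition.
- **Design & Methodology and Study Procedures, data collection:** keep the five items. At the first-week contact and every later one, in identical words for both arms, add one open question on any health problem or unplanned medical care for mother or baby since the last contact. Add specific items for an insertion-site problem, bleeding that led to medical care, and an infant visit or readmission, each with date and reason.
- **Criteria for discontinuation:** state that the events behind a discontinuation are recorded and counted in the arm to which the woman was randomised. The discontinuation rule itself is not at issue here.
- **Data Analysis:** report counts by arm with exact confidence intervals, and state the precision given above so that zero events are not read as evidence of no risk.
- **If Appendix B already asks these questions,** cite it in both data-collection sections.

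The cost is four questions on calls and REDCap forms that already exist, plus a few lines of protocol text. The downside is slightly longer calls.

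### Women are randomised before infant health is known and may then be discontinued or lose eligibility; the plan promises intention to treat but does not say that they stay in first-week follow-up and analysis

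*Combined protocol and SAP*

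**What the plan says.** Study Procedures fixes the moment of allocation: "When a study patient is admitted to L&D, they will be met by research personnel and be randomized to one of the two arms". Recruitment takes place before delivery, and the same section states: "The patient, provider, and research staff will be aware of arm allocation, this is not a blinded study".

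Criteria for selection of subjects contains two conditions that can be judged only after birth. One is for inclusion, "Pregnant women who delivery a healthy infant, regardless of gestational age", and one for exclusion, "Women who delivery infants that are not healthy".

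Criteria for discontinuation reads: "Participants who experience complications during labor and delivery or whose infants have medical problems will be discontinued". It continues directly: "Patients who change their mind about contraceptive implant use will be discontinued. Intention to treat analysis will be employed".

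Main problems anticipated says that enrolled women who have complications in labour, at delivery or afterwards cease to be eligible. It says separately that some women may decide against taking part.

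The primary outcome comes from daily contact starting 24 hours after delivery, for seven days or until lactogenesis, with contact after discharge until it occurs (Study Procedures). Data Analysis names only the software. No section defines *discontinued*, *complications* or the intention-to-treat set, and none gives a rule for a missing primary outcome.

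**The concern.** Allocation comes first, and some eligibility conditions are applied afterwards by people who know the arm. If *discontinued* means only that no implant is placed, intention to treat can be followed. If it means leaving the study, the primary comparison rests on a set of women formed after open-label allocation, and the intention-to-treat sentence cannot be carried out for those who left.

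The timing of the outcome makes this matter. Onset of lactation occurs within days of birth and is recorded to the nearest hour. If staff stop asking in the first week, the answer is hard to recover, so a later decision to analyse everyone may not repair the gap.

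Removals could also differ by arm. Arm 1 is treated within 2 hours of delivery and Arm 2 at 24 to 48 hours, so Arm 2 has longer for a change of mind or a newly found infant problem before insertion.

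**Working it through.** **Step 1. The three routes side by side.**
- *Labour or delivery complications.* Discontinued, and no longer eligible according to Main problems anticipated. This points to removal after allocation and conflicts with intention to treat. Complications are not listed among the selection criteria.
- *Infant problems.* Discontinued, and an exclusion criterion. This has the same implication and the same conflict.
- *Change of mind.* Ambiguous. One section speaks of changing one's mind about the implant, another of not wishing to take part. Later questionnaires record changes of contraceptive method, so changing method need not end follow-up.

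**Step 2. The plan's own figure.** Inputs from Number of subjects and statistical power: margin 12 h, SD 18 h, one-sided alpha 5%, power 80%, true difference 0. Allocation of 1:1 is assumed, because the ratio is not stated.

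n per arm = 2 × (1.645 + 0.842)² × 18² / 12² = 27.8, so 28 per arm and 56 in total. The plan states 68, which these inputs do not reproduce. The point here does not depend on that; the steps below take 68 as the number analysed.

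**Step 3. Precision and power.** SE = 18 × √(2/n). Power = Φ(12/SE − 1.645).
- 34 per arm: SE 4.37 h, power 86.5%.
- 41 per arm: SE 3.98 h, power 91.5%. This is a ceiling, since it assumes that all 82 women give an outcome, whereas the plan recruits 82 because it expects dropout.

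**Step 4. Shift from unequal removal.** The difference is taken as Arm 1 minus Arm 2, so non-inferiority requires the upper limit to lie below 12 h. Let k be the net excess of women removed from one arm and x the hours by which removed women are slower than retained women. Both are assumptions; the documents give neither. The shift is b = k × x / 41, and the SE is 4.37 h (68 analysed).
- More lost from Arm 2: power = Φ((12 − b)/SE − 1.645); false non-inferiority = Φ(−1.645 − b/SE).
- More lost from Arm 1: false non-inferiority = Φ(−1.645 + b/SE).

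| k | x | b | Arm 2: power | Arm 2: false non-inferiority | Arm 1: false non-inferiority |
|---|---|---|---|---|---|
| 1 | 6 h | 0.15 h | 85.8% | 4.7% | 5.4% |
| 1 | 12 h | 0.29 h | 85.0% | 4.3% | 5.7% |
| 2 | 12 h | 0.59 h | 83.4% | 3.8% | 6.5% |
| 3 | 12 h | 0.88 h | 81.7% | 3.2% | 7.4% |

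Equal removals, or removed women who are no slower, give no shift.

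**Step 5. Tipping points.**
- Power reaches 80% at b = 12 − (1.645 + 0.842) × 4.366 = 1.145 h. Times 41, that is about 47 woman-hours net from Arm 2, or about four women who are 12 h slower (47/12 = 3.9).
- False non-inferiority reaches 10% at b = (1.645 − 1.282) × 4.366 = 1.586 h. Times 41, that is about 65 woman-hours net from Arm 1, or between five and six such women (65/12 = 5.4).

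**The case against.** The best defence is that the plan already answers the question. The intention-to-treat sentence stands directly after the discontinuation rules, where its natural purpose is to say how those women are analysed. Daily monitoring applies to participants without exception. The loss of eligibility appears in a narrative section on anticipated problems, not in an analysis rule.

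Part of this stands. For a change of mind, the reading that intention to treat is preserved is as good as any other. For the other two routes it is not enough. The infant-health condition is a formal selection criterion, and a woman declared ineligible may no longer count as a participant to be called. Intention to treat needs outcomes, and no sentence secures them. The limitations section says that results do not extend to women with complications or infants with medical problems; that fits removal but does not prove it.

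Three stronger readings are tempting, and the documents do not support them.
- *The result will be biased towards non-inferiority.* Labour complications precede insertion and should be roughly balanced. The longer Arm 2 wait suggests more removals there, and if those women are slower, non-inferiority becomes harder to show.
- *The plan gives two randomisation times.* Design & Methodology refers to "Peripartum women with healthy, term newborns who plan to use the contraceptive implant" and continues "for postpartum contraception and intend to breastfeed will be randomized to receive". That is a summary of the population; only Study Procedures says when allocation happens.
- *A few missing outcomes could outweigh the margin.* Spreading each missing time over 24 to 168 h leaves (168 − 24)/41 = 3.5 h open per woman. But that window is not a bound, because contact continues until lactogenesis and women are asked when it occurred. It also sets a best-to-worst width against a one-sided margin. Measured from the plan's 54 h mean, four Arm 1 women all at 168 h move the difference by 4 × 114/41 = 11.1 h, and four Arm 2 women all at 24 h by 4 × 30/41 = 2.9 h. Neither reaches 12 h.

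**Conclusion.** The conflict is real and should be fixed. For complications and infant problems, following the plan as written points to removing women after open-label allocation, next to a promise of intention to treat. For a change of mind, the plan is unclear rather than contradictory. Nothing secures the first-week outcome of a discontinued woman on any route.

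The direction and size of any bias cannot be determined from the documents. The illustrated shifts, 0.15 to 0.88 h against a 12 h margin, are modest and rest wholly on the assumed 1 to 3 women and 6 to 12 h, with 1:1 allocation, SD 18 h and 68 analysed. The case for change therefore rests on the undefined analysis set and the hard-to-recover outcome, not on a predicted large bias.

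**What to change.** **Needed.** Reconcile Study Procedures, the selection criteria, Criteria for discontinuation and Main problems anticipated:
1. State that *discontinued* does not mean removal from follow-up or analysis.
2. Define the intention-to-treat set as all randomised women and name it as the primary analysis set.
3. Continue the daily milk question to day 7 or until lactogenesis for each of them, whether or not an implant is placed, unless she withdraws consent to follow-up.
4. State how missing primary outcomes are handled, with a sensitivity analysis.
5. Report discontinuations by arm and reason.

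This concerns follow-up and analysis only, not who receives an implant. It costs a short amendment and at most 7 contacts per retained woman through the existing system: 14 × 7 = 98 if the whole dropout allowance (82 − 68 = 14) were discontinued. It costs no power.

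**Optional, where feasible.** Open the envelope after delivery, once the existing healthy-infant criterion and the continued wish for the implant are confirmed. Events up to that point then precede allocation. The drawback is that supplies must be ready for every enrolled woman, because the arm is known only shortly before a delivery-room insertion. If complications are meant as an eligibility criterion, they should be defined among the selection criteria; they can precede allocation only under this option, and later events stay in the intention-to-treat set.

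**Optional.** Add a supportive per-protocol analysis using the recorded insertion times, since intention to treat alone can dilute a true delay in a non-inferiority trial. It needs one extra analysis of data already collected, and its set is not protected by randomisation.
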